5. STUDY ASSESSMENT AND PROCEDURES

This will be a collaborative study between Washington State University, Pillsy, Inc, and the clinical site Ideal Option (opioid and other substance use disorders treatment center). The overarching goal is to evaluate if the use of the Pillsy system will improve treatment adherence. The study coordinator will work closely with the medical assistant from the clinical site, conducting a scripted screening, by phone or in person, documenting substance use, addiction treatment history, medical and psychiatric history, medications and availability of social support. Only patients recently initiating BUP/NAL treatment will be approached to assess their eligibility for the study.

The clinical site will be responsible for the BUP/NAL prescription and treatment plan. Participants will receive their prescription medications through their normal pharmacy. Pillsy, though the RC will provide the Pillsy system which includes the smart bottle cap (Pillsy Cap), the mobile application (Pillsy App), and the SMS texting platform with a brief training on how to utilize the system. Pillsy Cap tracks when the bottle is opened or closed. Figure 1 (below) is a draft CONSORT diagram of participant flow through the study protocol.

[figure not shown]

Figure 1. Overview of study Procedures and CONSORT Diagram for Participant Flow.

Intervention

Participants will be directed to preferably bring their pill bottle and medication in for their baseline visits. While it is possible for us to orient participants to the intervention before they have received their prescription or after even if they don't have the bottle, this lessens the training experience substantially and could decrease the utility of the cap and efficacy of the system. The RC will orient the participants in the use of the Pillsy app. The participants in both groups will also have full access to the services normally provided by the prescribing office including blood testing and counseling services. The Pillsy intervention consists of a Smart Pill Cap and a mobile phone application. All participants will receive the Pillsy cap (to track pill bottle openings), but only the active group will receive the Pillsy app with messaging and reminders. Please note this when reading the below, since the below is what the PLY group will receive, but not the SAU group.

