If the patient does not take their medicine at the correct time, a light on the smart pill cap begins to flash. If the bottle is not opened within 20 minutes, the Pillsy application sends an SMS text reminder to the patient's phone. If the bottle is not opened within 60 minutes, the patient receives an automated phone call. The patient may also receive brief motivational phrases that can be tailored to patient needs and preferences. Pillsy also includes a "Pillsy Helpers" feature in which the patient can name friends and family members who will also receive a text message notification one hour after a missed dose. Thus, if the patient is struggling, his or her support system can attempt to contact the patient and offer motivation. Importantly, as proposed in the clinical trials detailed in this application, the MAT prescriber can also be a Pillsy Helper.

All data handling will conform to meet HIPAA requirements, including administrative, physical, and technical safeguards. Data will be encrypted in storage and in rest in REDCap with regularly scheduled data deposits from Pillsy into REDCap.

Participants in the service as usual (SAU) arm will receive a prescription for BUP/NAL tablets/sublingual films and any services normally provided by the prescribing office. Participants in the SAU arm will receive an "inactive" Pillsy smart cap that will track openings but will not provide reminders or any other messaging.

Screening Visit

The RC will screen the patient to assess the participant's appropriateness for the study. If the prospective participant meets inclusion/exclusion criteria, the RC will explain the clinical study in detail and informed consent will be obtained. If eligible, the participant will be trained on how to use the Pillsy system (cap and app) if randomized to PLY group. No training will be needed for the SAU. While their cap will be activated to capture open and close times, that is the only data that will be collected on the cap. and randomized to one of the study groups.

Week 1 Assessment

Study participants will return to office as frequently as the prescriber sees fit in the course of addiction treatment. At 1 week +/- 1 day, the RC will count BUP/NAL tablets/sublingual films and compare to the prescribed number of pills for that period. Participants will complete questionnaires.

Week 6 Assessment

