5.1.3 Other Safety Considerations

Data and Safety Monitoring Plan

Patients receiving opioid use disorder treatment will receive care as usual. Half of the participants will also receive the Pillsy intervention. The Pillsy intervention is a smart pill cap, mobile application with text and other messaging capability. We will keep enrollment to the lowest numbers possible that still allow sufficient power to answer research questions.

The risk to patients from the digital intervention is negligible. All data is collected in a HIPAA-compliant manner. Private identifiable information will be encrypted and kept secure.

Study visits will be conducted in a manner to protect participant privacy. The consent process, administration of questionnaires, etc. will occur in a private area. To reduce the risk of unauthorized disclosure of confidential information all personal identifiers will be kept separate from participant files and a study specific research identification number (key) will be assigned to each participant. Data will be collected, entered and accessed by study personnel trained in issues of confidentiality related to human subject protection. The key will be kept separate and not in the same enclave component of the network. Data will be entered into a password-protected database that is encrypted and firewalled. The consent form states that all information provided by the participant will be kept private except in the case that this would immediately put the participant or someone else in danger. In that case the Investigator would release information to keep the participant or another person safe. The consent states that if

Investigator learn about abuse to a child or an elder, that information must be reported to the proper authorities.

As in all research of this nature, there is the possibility of discomfort or embarrassment related to questions dealing with opioid use and social stigma for engaging in these types of behaviors. Participants will be informed that they have the right to refuse to answer any question. If participants find any aspects of their involvement in the research study particularly distressing, they will be encouraged to discontinue participation.

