Changes to the study protocol may result in the need for a new consent form. Only the approved and most recent consent form will be used. The consent form document will have an IRB stamp of approval, version number and date at the bottom each page.

Please note: Unless you have the PI's authorization, do not conduct the consenting process.

Consenting Process:

1. The consenting process will be conducted in a consistent manner for every potential participant.
2. If participant is eligible, the iPad that was used for screening will display the consent form. RA or RC will explain that this document will explain the details of the study they are being asked to take part in. Allow the participant plenty of time to read.
3. When the participant is done reading the consent, they will be asked if they have any questions about the study. All questions will be answered before the participant signs the informed consent document. The consent form will then be thoroughly reviewed to ensure that the participant understands what they are agreeing to. Participants will be asked to type in their name and date for the consent electronically, and actually sign their name electronically.
4. Eligibility for the study is determined by study procedures. Signing the consent does not ensure eligibility to participate. That said, it will be made clear to the prospective participant that participation will not impact their care.
5. The most key point to stress in the consenting process is that participation is voluntary. Moreover, continued involvement in the study is also voluntary. Participants can choose not to consent to the study or discontinue at any time for any reason. They can choose not to answer any questions that make them feel uncomfortable.
6. Show the participant where to type their name and date the consent form. The participant must date and initial the consent and be offered a paper copy of the consent to the participant for their records.
7. Remember that consenting is an ongoing process.

SUICIDAL & HOMICIDAL IDEATION/BEHAVIOR

If a person reveals SUICIDAL IDEATION (in the last 30 days) at any level or during the screening:

1. Staff will explain their concern for the subject and inform their supervisors.
2. All current (last 30 days) suicidal ideation and behavior concerns will be immediately reported to "911" or appropriate clinic staff so that their protocol can be initiated.

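### The distress rule in section 5.1.3 does not separate stopping the app or questionnaires from leaving follow-up, so loss of the primary outcome may differ by arm

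*Combined protocol and SAP*

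**What the plan says.** Section 5.1.3 first names the expected source of distress: "there is the possibility of discomfort or embarrassment related to questions dealing with opioid use and social stigma". It offers a limited remedy, "Participants will be informed that they have the right to refuse to answer any question", and the Consenting Process in section 8 repeats it: "They can choose not to answer any questions that make them feel uncomfortable". Section 5.1.3 then adds a wider rule, which applies to any aspect of the study: if participants find one "particularly distressing, they will be encouraged to discontinue participation".

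The Intervention text in section 5 gives both arms a tracking cap but says that "only the active group will receive the Pillsy app with messaging and reminders". For the Pillsy arm, a flashing light is followed by a text at 20 minutes, and then "If the bottle is not opened within 60 minutes, the patient receives an automated phone call". Named friends and family "will also receive a text message notification one hour after a missed dose".

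The primary outcome is the medication possession ratio. The research coordinator counts tablets or films at weeks 1, 6 and 12 (section 5). When a participant stops engaging, section 5 provides for at most two telephone attempts at an exit interview. Section 6.4 uses dropouts' data only until withdrawal and favours likelihood methods or multiple imputation. Section 6.3 specifies an intention-to-treat primary analysis.

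**The concern.** The right to withdraw is already secured in section 8. The rule in 5.1.3 goes further, because staff are to encourage leaving, and the only milder response described is to decline a question. That helps someone upset by a question. It does not help someone upset by an automated call or by a text sent to a relative.

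Those features exist in one arm only, and they follow a dose not taken on time. If they cause marked distress, the exits would come from the Pillsy arm and could be related to adherence, which is what the trial measures. The primary outcome would then be missing in an arm-related way while section 6.3 promises an intention-to-treat comparison. The third objective in section 3, to learn where participants resist Pillsy, would also lose later assessments from people well placed to inform it.

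**Working it through.** **Inputs.** From the documents: 15 per arm (section 6.1); pill counts at weeks 1, 6 and 12 (section 5); two-sided tests and 95% intervals (section 6.2). Assumed, because the documents give no value: the number *k* of extra Pillsy exits, the gap *d* in possession ratio between stayers and leavers, the standard deviation (SD) of the ratio, and alpha 0.05.

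**The plan's own figure.** Section 6.1 takes 15% of a Phase II total of 200: 0.15 × 200 = 30, or 15 per arm. This reproduces. No Phase I power is stated. The 25% attrition belongs to the Phase II calculation and is not split by arm or reason.

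**Which sources of distress have a step short of leaving?**

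| Source | Exposed | Step described short of leaving |
|---|---|---|
| Questions on opioid use and stigma | Both arms; Table 1 has one schedule | Decline the question |
| Motivational phrases | Pillsy only | Can be tailored |
| Light, reminder texts, automated calls | Pillsy only | None |
| Helper notices | Pillsy only | Participant names the Helpers; no way to stop the notices is described |

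**What ends on leaving.** The coordinator's counts have no described continuation after withdrawal. Clinic data reach the university under a data use agreement (section 5, Laboratory Assessment), but the pill count is not part of clinic data. Section 5.1.3 speaks of being discontinued from the Pillsy intervention when a provider stops BUP/NAL. The protocol therefore has wording for stopping the intervention alone, but does not use it in the distress rule or say whether counts then continue.

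**Illustrative shift.** If stayers average *m* and *k* leavers average *m* − *d*, the full-arm mean is *m* − (*k*/15)*d* and the observed-case mean is *m*. The shift is (*k*/15) × *d*.

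- *k* = 1: 1/15 = 6.7% of the arm.
- *k* = 2: (2/15) × 0.10, 0.30, 0.50 = 0.013, 0.040, 0.067.
- *k* = 3: (3/15) × 0.10, 0.30, 0.50 = 0.020, 0.060, 0.100.
- *d* = 0: no shift, whatever *k* is.

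**Would an imbalance be recognisable?** With equal withdrawal probabilities of 5%, 10% or 25% in two arms of 15 (independent binomials), Pillsy exits exceed control exits by two or more with probability 0.09, 0.17 or 0.26. A small imbalance would therefore not by itself show an arm effect, which is a reason to record causes.

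**Precision.** For a difference of 0.20 (normal approximation), power at 15 v 15 is 0.78 with SD 0.20 and 0.45 with SD 0.30. At 12 v 15 it is 0.73 and 0.41. The loss of precision is small, so the issue is possible bias.

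**The case against.** The strongest reply is that the rule protects participants and has a high threshold: the experience must be particularly distressing, and disliking a reminder does not qualify. The distress that 5.1.3 names comes from questions not split by arm, and the section calls the intervention's risk negligible. The analysis is also not a simple mean of completers. Section 6.2 plans repeated-measures methods such as generalized estimating equations, and section 6.4 adds likelihood methods or imputation, so counts made before exit are used. Reasons for leaving are sought through the exit interview and the reason-for-quitting item in Table 1, and 5.1.3 seeks feedback from discontinued participants. The consent pages were not available for review and may contain partial-withdrawal options.

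Most of this stands, and it rules out several stronger readings. A reader might infer that the rule will fall mainly on the Pillsy arm. The documents give no rate by arm, so this is plausible but not established. A reader might infer that nothing lies between full participation and exit, but declining questions does. A reader might infer that leavers are necessarily poor adherers. The trigger is distress, and texts also go out for doses taken late. A reader might take an example such as 12 stayers at 0.80 and three leavers at 0.40, with a full-arm mean of (12 × 0.80 + 3 × 0.40)/15 = 0.72, as showing an 8-point overstatement. Those values are assumed, and the calculation ignores the planned methods.

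The reply does not supply a described route for stopping the messaging while remaining in pill-count follow-up. Nor does it give an analysis for loss that depends on unseen outcomes: the planned methods recover little for someone who leaves soon after week 1.

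**Conclusion.** The concern holds as a gap in the follow-up rule. As written, 5.1.3 steers markedly distressed participants towards leaving, and the documents do not distinguish giving up the app or questionnaires from giving up outcome collection. Loss of the primary outcome may therefore be greater in the Pillsy arm and may be related to adherence. Neither is shown to occur. The size is unknown, and the shifts calculated above are sensitivity values for an observed-case mean that depend wholly on the assumed number of exits and adherence gap. They do not estimate the bias of the planned analysis. In a proof-of-concept study of 30 the effect would be modest unless several Pillsy participants left with clearly lower adherence. The change is still worth making, because the loss is partly avoidable and the remedy is cheap.

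**What to change.** Replace the distress sentence in 5.1.3 with a rule on participation and data collection that says:

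- a distressed participant may stop the questionnaires, or the app and its messaging, without leaving the study;
- with the participant's agreement, the week 1, 6 and 12 pill counts and the clinic records continue to be collected and are analysed in the randomised arm;
- full withdrawal remains available at any time without penalty.

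Record what was stopped, when and why. Reconcile the distress and discontinuation wording in 5.1.3, the analysis set in 6.3, the dropout statement in 6.4 and the consent form with this rule. It concerns study data only and leaves decisions about BUP/NAL care where they are.

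The cost is a few sentences, matching consent wording if it is not already there, and one REDCap field. Some Pillsy participants would be followed with reduced messaging, which slightly dilutes the contrast but keeps the intention-to-treat estimate.

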6. STATISTICAL CONSIDERATIONS

6.1 Sample Size

For this Phase I study we are planning to randomize 15% of the targeted N (200) of a full-scale Phase II study, resulting in a total of 30 subjects, 15 per arm. More than anything, this is designed as a “proof-of-concept” study to demonstrate that Pillsy can produce some amount of adherence improvement and is both feasible and useful to patients so we can plan a larger version of this study in Phase II.

Sample size calculations – Our choice of sample size for the Phase II trial (n=200) was based on power calculations for detecting a 20% increase in our primary outcome of increasing adherence to BUP/NAL while also considering treatment retention assessed by office visits and assuming a 25% attrition rate in our cohort. This translates to an OR of 2.4, which we would have 99% power to find based on 3 longitudinal assessments and assuming we are examining the between effect only. Using a more conservative estimate of a 10% change, we would still have 90% power to detect this effect (OR of 1.6).

6.2 Statistical Analyses

Results will be presented as means, medians, and ranges for continuous variables and as totals and percentages for categorical variables. All significance tests will be 2-tailed, and all

confidence intervals will be presented with 95% degree of confidence. Differences in the quantitative responses at the baseline assessment will be statistically analyzed using Student's t test for two groups. Repeated measures tests will be used for longitudinal data, e.g., generalized estimating equations, including our primary and secondary outcomes. When the null hypothesis is rejected by primary analysis, appropriate post hoc analyses will be used.

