1. PROTOCOL SUMMARY

1.1 SYNOPSIS

Title: Mobile Medication Adherence Platform for Buprenorphine-Naloxone (MAP4BUP) During Treatment of Opioid Use Disorder: Phase I MAP4BUP Study

Opioid misuse and abuse affect the health and the well-being of millions of Americans. On average, 130 Americans die every day from an opioid overdose in 2017, according to CDC data. Opioid agonist therapy, such as buprenorphine-naloxone (BUP/NAL), can reduce opioid overdose deaths, decrease opioid misuse, and improve quality of life. Unfortunately, poor medication adherence is a barrier to long term efficacy of this therapy. To assess compliance, we plan to substantially monitor adherence to inexpensive oral buprenorphine-naloxone with Pillsy, a Bluetooth-connected smart pill cap and pharmacy software platform. The technology platform was developed over the past three years using principles of behavioral science, modern design, and highly scalable wireless and mobile technologies.

We will build out and adapt our current Pillsy platform, then test it in a small-scale trial to assess feasibility, usability, and effectiveness. We propose, in Phase I, to conduct a study involving 30 subjects selected randomly among patients prescribed (BUP/NAL) for opioid misuse to better understand their willingness to use Pillsy and identify areas of problematic compliance. Using the data obtained in Phase I and after meeting with the FDA, we will further refine the platform in Phase II. This will be a collaborative study between Washington State University, Pillsy and the clinical site Ideal Option.

The purpose of this randomized, controlled trial in Phase I is to determine whether the Pillsy intervention can improve adherence to BUP/NAL compared to services as usual (SAU). The primary endpoint will be adherence to MAT as determined through the medication possession ratio at the end of the trial. The hypothesis is that the Pillsy intervention will significantly improve adherence to medication-assisted treatment (MAT) compared with SAU.

Study Design

Narrative Study Description

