The research coordinator (RC) will provide the Pillsy device and orient the participants in the use of the Pillsy app. Participants in both groups will also have full access to services normally provided by the prescribing office including blood testing and counseling services (i.e. SAU). All participants will receive the Pillsy cap (to track and time stamp pill bottle openings, closings, etc). The participants assigned to the Pillsy intervention, will also have a mobile phone reminder application. If the participant does not take their medicine at the correct time, a light on the smart pill cap will flash. If the bottle is not opened within 20 minutes, the Pillsy app sends an SMS text message to participant's phone. If the bottle is not opened within 60 minutes, the participant then receives an automated phone call. The participant may also receive brief motivational phrases or craving surveys that can be tailored to participant needs and preferences.

Pillsy also includes a Pillsy Helpers feature in which the participant can name friends and family members who will also receive a text message notification one hour after a missed dose. If the participant is struggling, his or her social support can attempt to contact the participant. The MAT prescriber may also be a Pillsy Helper. The MAT prescriber may be contacted when the participant has missed a dose if they are designated as a helper, giving the prescriber the opportunity to intervene. Providers may decide to call the imminently nonadherent participant to provide a brief, timely therapeutic intervention for which the provider can bill using the 99091 CPT code.

All data handling will conform to appropriate regulatory guidelines (HIPAA) and will be collected in such a way that it can be integrated into existing EMRs. The long-term goal is for this information to be available to one's prescriber and provider in real-time for monitoring.

Participants in SAU arm will receive a prescription for BUP/NAL tablets/sublingual films and any services normally provided by the prescribing office. Participants in SAU arm will receive an inactive Pillsy smart cap that will track openings but will not provide reminders or any other messaging.

Primary Endpoint

Adherence to BUP/NAL treatment assessed by medication possession ratio (pills taken/pills prescribed)

Secondary Endpoints

1. Participant engagement quantified through office visits and assessed via real time surveys

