referred for follow-up with a RC. The RC will contact the patient and assess the participant's appropriateness for the study in a screening interview. The RC will explain the clinical study in detail and will obtain informed consent. All potential participants will be given plenty of time to read the consent form. They will have time to ask questions and their questions will be answered to their satisfaction by the study RC, the Principal Investigator, or the Co-investigator.

After ensuring the potential subject has understood his/her role in the study, then he/she will be requested to sign and date the Institutional Review Board (IRB) approved Informed Consent Form (ICF), after which a screening number will be assigned. The consenting process should be conducted at the clinic's site and in a consistent manner for every potential participant.

The consent process for this study will include a video demonstration of handling of the Pillsy cap and how the Pillsy system works to aid in the subject's and study subject partner's understanding of this technology. If the participant meets inclusion/exclusion criteria, he/she will be randomly assigned to one of the two arms of the study.

Method of Assigning Subjects to Study Arms: Randomization

Subjects will be centrally registered and randomly assigned 1:1 to the PLY or SAU group. We will use permuted block randomization and stratify on 1) age, 2) sex, and 3) severity of OUD (mild, moderate, severe) based on DSM-5 criteria for diagnosis of opioid use disorder (Mild: 2-3 symptoms. Moderate: 4-5 symptoms. Severe: 6 or more symptoms).

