Study participants will return to office as frequently as the prescriber sees fit in the course of addiction treatment. At 6 weeks +/- 2 days, the RC will count BUP/NAL tablets/sublingual films and compare to the prescribed number of pills for that period. Participants will complete questionnaires.

Week 12 Assessment

Study participants will return to office as frequently as the prescriber sees fit in the course of addiction treatment. At 12 weeks +/- 3 days, or RC will count BUP/NAL tablets/sublingual films

and compare to the prescribed number of pills for that period. Participants will complete questionnaires.

Ongoing Assessments

Pillsy will continuously collect data on pill bottle openings, missed doses, text messages sent, automated phone calls made, etc. If there is a loss of contact, or the participant stops their engagement with the study, the RC will attempt to contact the participant (up to two (2) attempts) with an exit interview, by phone. If no answer, no message will be left. The coordinator will attempt to call again 2-3 business days later for a final attempt to describe reasons for withdrawal from the study.

Table 1. Schedule and Types of Assessments Performed: MAP4BUP Phase I.

	Screening/Baseline	Week 1	Week 6	Week 12
Informed consent	X			
Verify inclusion/exclusion criteria are met	X			
AUDIT	X			
Demographics	X			
Fagerström	X			
Addiction Severity Index – Lite	X			
Timeline Follow-Back of medication use and drug and alcohol use	X	X	X	X
DSM-5 OUD Checklist*	X			
Pill/film count and self-report of prescriptions	X	X	X	X
Barratt Impulsiveness Scale (BIS) 8	X	X	X	X
Opioid Craving Scale	X	X	X	X
Healthy Days Core Module (CDC HRQOL-4)	X	X	X	X
Sleep Related Impairment	X	X	X	X
Sleep Disturbance	X	X	X	X
Pain Intensity	X	X	X	X
Pain Interference	X	X	X	X
Standard counseling, prescribing, dose changes**	As needed, determined by prescribing provider and medical team.			
Pillsy System Usability Questionnaire		X		X
Adverse event monitoring	X	X	X	X
Reason for quitting	Administered once, triggered by predefined non-adherence to the treatment.			

*Diagnostic and Statistical Manual of Mental Disorders, Fifth Edition (DSM-5) Opioid Use Disorder (OUD) research checklist

**To be guided by the discretion and standard practices of the prescriber.

Laboratory Assessment

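### Section 6.2 names only GEE, as an example, for 30 participants, with no small-sample method and no contrast that yields the end-of-trial MPR

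*Combined protocol and SAP*

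**What the plan says.** The synopsis (1.1) states: "The primary endpoint will be adherence to MAT as determined through the medication possession ratio at the end of the trial". It defines the measure as "Adherence to BUP/NAL treatment assessed by medication possession ratio (pills taken/pills prescribed". The hypothesis is one of significance: "The hypothesis is that the Pillsy intervention will significantly improve adherence to medication-assisted treatment (MAT) compared with SAU".

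Section 5 has the coordinator count tablets or films at weeks 1, 6 and 12 and, each time, "compare to the prescribed number of pills for that period". Table 1 leaves "Standard counseling, prescribing, dose changes" to the prescriber throughout.

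Section 6.1 sets the size, "resulting in a total of 30 subjects, 15 per arm", and calls the study a proof of concept meant to inform Phase II.

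Section 6.2 covers the analysis in one sentence: "Repeated measures tests will be used for longitudinal data, e.g., generalized estimating equations, including our primary and secondary outcomes". It also makes all tests two-sided, promises 95% intervals, and allows post hoc analyses once the primary null is rejected. The only other test it names is Student's t, for baseline differences. No link, working correlation, variance estimator, reference distribution or visit contrast appears anywhere. Section 6.4 leaves missing data to maximum likelihood or multiple imputation.

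**The concern.** Two things are left open, and the first decides how much the second matters.

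- **Contrast.** The end-of-trial MPR could be one ratio over all 12 weeks or the ratio for the last counting interval. The documents do not say which, nor whether each count is per interval or cumulative. A repeated-measures model could report a visit-averaged arm effect, a week-12 contrast or an arm-by-time test. These are different quantities, and a contrast left open can be chosen after the data are seen.
- **Small sample.** The ordinary GEE sandwich variance is biased downward when there are few participants. With 15 per arm, an uncorrected analysis would reject too often and give intervals that are too short.

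At stake are the primary significance test and the precision attached to the estimate carried into Phase II planning.

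**Working it through.** **Inputs.** Section 6.1: 15% × 200 = 30, so 15 per arm; the plan's figure reproduces. Section 6.2: two-sided tests and 95% intervals; no alpha is stated, so 5% is inferred from the interval level. Section 5: counts at weeks 1, 6 and 12, hence intervals of 1, 5 and 6 weeks if counts are per interval. Assumed, because the documents are silent: uncorrected sandwich with a normal reference, between-visit correlation 0.5, the outcome distributions, and 25% dropout (the Phase II attrition figure in 6.1).

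**Closed form.** With complete data and arm as the only covariate, the GEE arm effect is a difference of two means. The uncorrected sandwich divides each arm's sum of squares by n instead of n − 1. A z test therefore rejects when a t statistic on 2n − 2 df exceeds 1.96 × √((n − 1)/n).

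- n = 15: 1.96 × √(14/15) = 1.8935. Type I error = 2 × P(t₂₈ > 1.8935) = 6.87%, so coverage is 93.1%.
- Interval width relative to correct: 1.8935 / 2.0484 = 0.924, about 8% too narrow.
- n = 11 (15 × 0.75 = 11.25, rounded down): 7.64%.

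**Corrections at n = 15.**

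- Kauermann-Carroll multiplies the variance by n/(n − 1). With a t reference this is the two-sample t test: 5.0%, width ratio 2.0484 / 1.8935 = 1.082.
- Mancl-DeRouen multiplies it by (n/(n − 1))². With a t reference the threshold is 2.0484 × √(15/14) = 2.1203: 4.3%, width ratio (15/14) × (2.0484/1.96) = 1.120.

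**Simulation.** 15 per arm, 3 visits, 10,000 runs per case (Monte Carlo error about 0.25 points). The continuous MPR was normal or skewed; the binary MPR had rates 0.5 to 0.85. Rejection rates under the null, in percent:

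| Case | Uncorrected, z | Kauermann-Carroll, t | Mancl-DeRouen, t |
|---|---|---|---|
| Continuous, visit-averaged, complete | 6.7–6.9 | 4.7–5.1 | 4.1–4.5 |
| Continuous, visit-averaged, 25% dropout | 6.7–7.1 | 4.9–5.1 | 4.3 |
| Continuous, week 12, complete | 6.7–7.0 | 4.7–5.0 | 4.1–4.4 |
| Continuous, week 12, 25% dropout | 7.6 | 5.3–5.5 | 4.3–4.4 |
| Binary (logit), visit-averaged, complete | 5.7–6.2 | 3.9–4.2 | 3.2–3.5 |

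A separate binary run of 1,000 trials at rate 0.6 gave 6.9% uncorrected at 15 per arm and 5.8% at 11 per arm. Its Monte Carlo error is about 0.7 points, too coarse to refine the last row. A two-sample t test on one whole-trial MPR per participant rejected 4.9% of the time in 20,000 runs.

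**Contrast.** A visit-averaged effect gives each count one third of the weight, given complete data and an independence or exchangeable working correlation. The first count covers 1 of 12 weeks. For illustrative arm differences by interval, in percentage points with constant daily pills:

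| Pattern | Visit average | Whole trial | Final interval |
|---|---|---|---|
| 0 / 10 / 15 | 25/3 = 8.3 | (0×1 + 10×5 + 15×6)/12 = 11.7 | 15 |
| 15 / 10 / 5 | 30/3 = 10.0 | (15×1 + 10×5 + 5×6)/12 = 7.9 | 5 |
| 10 / 10 / 10 | 10 | 10 | 10 |

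Day weights are themselves not fixed. If daily pills were 2, 2 and 1 in the three intervals, the first pattern's whole-trial value would be (0×2 + 10×10 + 15×6)/18 = 10.6.

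**Scale.** The correct 95% half-width is 2.0484 × SD × √(2/15): 11.2 points for an SD of 15 and 22.4 for an SD of 30 (SDs assumed). A shortfall of 1 − 0.924 = 7.6% is then about 0.9 to 1.7 points.

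**The case against.** The other side has real weight.

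- **The plan commits to nothing faulty.** A reader might infer that it has chosen a test with inflated error. The documents do not support that: GEE is offered as an example, no variance estimator is named, and the maximum likelihood option in 6.4 fits a mixed model equally well. The 6.9% is conditional on a default that the plan does not state.
- **The outcome may be binary.** Section 6.1 expresses effects as odds ratios, which points that way, although that text concerns Phase II and the synopsis defines a ratio. For a binary MPR the inflation in the main simulations is only 0.7 to 1.2 points, and both corrections over-correct. This stands.
- **It is a proof of concept.** An interval short by 1 or 2 points beside a half-width of 11 to 22 would hardly alter a Phase II plan. This stands as a limit on importance. The stated hypothesis is still one of significance, and a 95% interval should cover at its stated rate.
- **The choice of correction is partly preference.** Mancl-DeRouen with a normal reference gave 5.0 to 5.3% at 15 per arm in separate simulations. This too stands.

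Three other stronger readings should be resisted.

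- One is that the primary outcome is not linked to the repeated-measures analysis at all. The 6.2 sentence does cover it; only the time point and contrast are missing.
- Another is that a visit average matches the end-of-trial effect only when the effect is constant. Effects of 5 / 15 / 10 average to 10, which is also the final-interval value, so constancy is sufficient but not necessary.
- The third is that a stratified design ("We will use permuted block randomization and stratify on 1) age, 2) sex, and 3) severity of OUD") implies a covariate-adjusted model with greater inflation. No such model is described.

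The between-arm effect mentioned in 6.1 belongs to the Phase II power calculation and does not settle the Phase I contrast.

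**Conclusion.** The point holds as a cheap improvement, not as a fatal flaw. The plan does not say how its repeated-measures analysis produces the end-of-trial MPR, and the only method it names needs a small-sample correction at this size. Under an uncorrected sandwich with a normal reference and a continuous MPR at 15 per arm, the error rate is about 6.9% and intervals are about 8% too narrow. With 25% dropout, the simulated week-12 contrast reaches 7.6%.

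The visit-averaged and end-of-trial effects agree if the effect is constant over time, and otherwise only by coincidence. The size of any gap depends on a trajectory that nobody yet knows. The contrast comes first logically: if the endpoint is one whole-trial ratio per participant, the primary outcome has no repeated measure and the sandwich problem disappears.

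**What to change.** 1. State whether the end-of-trial MPR is whole-trial or final-interval and whether counts are per interval or cumulative, and name that quantity as the single primary contrast.
2. **If whole-trial:** compute total pills taken over total pills prescribed for each participant, without fixed day weights because dose changes are allowed. Compare arms in a two-arm linear model with a t reference.
3. **If final-interval:** fit an arm-by-visit model to the per-interval MPR and test the week-12 arm contrast. Use either a mixed model with Kenward-Roger df (consistent with maximum likelihood in 6.4) or a GEE with a bias-corrected sandwich and a t reference, on 28 df with arm as the only participant-level covariate. With GEE, impute missing counts by multiple imputation, which 6.4 already allows.
4. State whether MPR is analysed as continuous or dichotomised.

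The cost is a few sentences and a software option, with no extra participants or visits. Compared with uncorrected GEE, intervals are about 8% wider with Kauermann-Carroll and t, and about 12% wider with Mancl-DeRouen and t. For the week-12 contrast with 25% dropout the figures are 9% and 14%. For a continuous MPR, Kauermann-Carroll stayed closer to 5%. For a binary MPR both are somewhat conservative (3.9–4.2% and 3.2–3.5%).
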